Eligible participants will be randomised to receive either 7-day atorvastatin 20mg (25 participants), or 7-day placebo (25 participants) administration. Randomisation will occur on the day of screening, or up to a maximum of 4 weeks after screening. Randomisation after the Screening Visit will occur in the event that further information is needed before determining whether participants are eligible to take part (for example, if a participant needs to follow-up with details of allergies, or previous studies they have taken part in). In this case, if more than 4 weeks have elapsed, another Screening Visit will be performed to ensure participants are still eligible. The randomisation code will be drawn up by a researcher not involved in the study using an online randomisation tool (<https://www.sealedenvelope.com/simple-randomiser/v1/lists>). Randomised participants will be given 7 days of the drug to take home, as well as full instructions of how and when to take them.

The atorvastatin drug and the placebo will be provided by the Oxford Pharmacy Stores and will be encapsulated at the Neurosciences Building according to previously agreed standard operating procedures (APPENDIX G: Neurosciences, SOP Number: Encapsulation Version 2: 22.10.2012). Blinding will be achieved by the identical matching of the atorvastatin and placebo treatments. Participants will not be aware of the treatment that they will be receiving; neither will the researcher, as this study is double-blind.

Allocation of treatments will be recorded on a Randomisation List, which will be updated when each new participant enters the randomised phase. The list will be held at the Neurosciences Building by a scientist uninvolved in the study.

The study medication and placebo will be stored in a secure environment at the Neurosciences Building accessible only to staff. It will be stored at room temperature and accounted for using agreed study documentation. Using the Randomisation List and the participant's unique randomisation code, staff will determine whether to dispense active or placebo tablets.

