The randomisation code will be broken if a participant requires treatment for a new medical condition or experiences serious adverse reactions and either of these situations make it clinically important to know what medication they are taking. A 24/7 emergency mobile contact number will be provided on a wallet-sized card given to participants during their Research Visit. The research team member on-call will be able to contact the medical supervisor and they will make the decision to unblind. In order to unblind the participant, the medic will access the list kept in a secure cabinet at the Neurosciences Building and will disclose the allocation within a maximum of one hour. If breaking the code is necessary, only the individual's code will be broken. Data from unblinded participants will not be admitted to analysis. If unblinding occurs, the researcher will record the reason and result of the unblinding, as well as the date and time of the event.

During the week of drug/placebo administration, participants will be advised not to drink alcohol and not to carry out activities requiring full alertness, such as driving, if they are aware of any impairment. During this week, a researcher will phone up the participant on day 2 and day 4 to check that there are no concerns. Additionally,

participants will receive a text message every day reminding them to take the study medication. They will have the 24-hour contact phone number of a member of the study team and be encouraged to get in contact if they have any concerns or queries during the study week, or if their medication or health status changes.

Subsequent Visits

The Research Visit (approximately 2 hours) will take place after day 7 of atorvastatin/placebo administration. This visit will involve administration of behavioural tasks measuring emotional and reward processing. It will take place at the Neurosciences Building, Warneford Hospital.

Participants will complete the following questionnaires before the behavioural tasks:

- Positive and Negative Affect Schedule (PANAS)
- Side-effects questionnaire
- State Anxiety Inventory (state-STAI)
- Visual Analogue Scales (VAS)

Also, phlebotomy will be repeated to obtain a sample of:

- high sensitivity-C Reactive Protein

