7. INTERVENTION(S)

a) Drug/Substance 1

Name of drug/substance to be used	Atorvastatin
Formulation and route of administration for study	20mg atorvastatin tablets will be encapsulated in opaque capsules
Dose and route of administration for study	20mg atorvastatin once daily at night-time, oral dose
Duration of treatment for study	7 days
Licence status of this drug/substance	Atorvastatin is a licensed drug
Usual Indication	Atorvastatin is usually indicated in adult patients with primary hypercholesterolaemia, or combined (mixed) hyperlipidaemia in adult patients who have not responded adequately to diet and other appropriate measures, in adult patients with homozygous familial who have not responded adequately to diet and other appropriate measures, and in adult patients with atherosclerotic cardiovascular disease or diabetes mellitus for prevention of cardiovascular events
Usual Dose	10-80mg once daily, at night-time

Usual duration of treatment	Life-long
Where will drug/substance be sourced from?	Oxford Pharmacy Stores
Where will drug/substance be stored?	Atorvastatin will be stored within the Neurosciences Building, Warneford Hospital. It will be stored at room temperature in a locked cupboard, which is suitable for drug storage.
How will drug/substance be dispensed?	Atorvastatin will be dispensed from the Neurosciences Building, Warneford Hospital by a study medic or nurse.
How will the drug/substance be prepared by the researchers for use in this study?	Atorvastatin will be encapsulated by trained clinical trial support staff using our Standard Operating Procedure (APPENDIX G: ENCAPSULATION STANDARD OPERATING PROCEDURE).

b) Drug/Substance 2 (or placebo)

Name of drug/substance to be used	Lactose Placebo
Formulation and route of administration for study	Placebo tablets will be encapsulated in opaque capsules
Dose and route of administration for study	One capsule once daily at night-time, oral dose
Duration of treatment for study	7 days
Licence status of this drug/substance	N/A
Usual Indication	N/A
Usual Dose	N/A
Usual duration of treatment	N/A
Where will drug/substance be sourced from?	Placebo tablets will be sourced from HSC (www.hsconline.co.uk).
Where will drug/substance be stored?	Placebo will be stored within the Neurosciences Building, Warneford Hospital. It will be stored at room temperature in a locked cupboard, which is suitable for drug storage.

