During the week of drug/placebo administration, participants will be advised not to drink alcohol and not to carry out activities requiring full alertness if they are aware of any impairment. During the week of drug/placebo administration, a researcher will phone up the participant on day 2 and day 4 to check that there are no concerns. Participants will have the 24-hour contact phone number of a member of the study team and be encouraged to get in contact if they have any concerns or queries during the study week, or if their health status changes. The named researcher will in turn contact a qualified medical doctor if necessary.

Give details on the medical cover required and who will provide this cover	
A medical doctor who is part of the research team will review the screening and make a final judgment about including participants in the study. A qualified medical doctor will be contacted if a participant expresses concern to a named researcher regarding side-effects or health status changes during the study week.	
Will the participants' GP be informed about their participation in the study? If not, please justify	
Participants' GPs will not be informed about their participation in the study. Seven days of atorvastatin 20mg administration is not regarded as a clinically significant intervention and is not expected to have any impact on participants' health or wellbeing. We are excluding participants who are pregnant, breastfeeding, women of child-bearing potential not using appropriate contraceptive measures, or people who have any medical conditions for whom the study would not be suitable.	
What is your planned procedure if an incidental finding is suspected?	
Participants will be screened to exclude those with past or current psychiatric symptoms and Best Practice Guidance (BPG) 08 (Psychological distress) will be followed in order to ensure best practice in situations where participants with psychological distress are identified. The guidance in this document around confidentiality and researcher's training will also be adhered to.	
If an incidental finding has clinical implications, what action will you take?	

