Statins are considered extremely safe drugs: their more common side-effect are muscle pain or weakness (usually mild and quickly responding to stopping or switching medication) and elevation of liver transaminases (significant only in case of pre-existing hepatic disease), whereas more serious adverse events include rhabdomyolysis (very rare but severe myopathy associated with elevated creatine kinase and myoglobinuria), new-onset diabetes mellitus (in predisposed individual with pre-existing hyperglycaemia), and haemorrhagic stroke (in patients with prior haemorrhagic stroke or lacunar infarct); however, clinical trials have ultimately concluded that such adverse events attributed to statin therapy in routine practice are not actually caused by it (Collins-2016), especially at doses lower than 80mg/day and when used for less than 52 weeks (Li-2016). Other common ($\geq 1/100$, $< 1/10$) but usually mild side-effects include: nasopharyngitis, pharyngo-laryngeal pain, epistaxis, headache, and gastrointestinal disturbances (constipation, diarrhoea, flatulence, dyspepsia, nausea). The potential side-effects and adverse events will be clearly stated in the Participant Information Sheet and researchers will discuss these with participants as part of the informed consent procedure.

To minimise the risk associated with side-effects, participants will be contacted on days 2 and 4 of the study week by a named researcher to check there are no concerns. All participants will have 24-hour contact details of a named researcher who they can contact during the study period. The named researcher will in turn contact a qualified medical doctor if necessary. In order to limit the risks associated with fatigue, during the week of statin/placebo administration, participants will be advised not to drink alcohol, and not to carry out activities requiring full alertness if they are aware of any impairment.

If judged necessary by the medical lead, the randomisation code will be broken for that individual by the medical supervisor and the participant will be advised to stop taking the medication and withdrawn from the study.

Will the research involve deliberate deception of participants?
 
If yes, justify why deception is used, describe deception and debriefing process, and include debriefing documents in the application
	Yes 	No 
---	------------------------------	--

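### The wallet card with the 24/7 emergency number is handed over at the Research Visit, after the seventh dose; it should be given when the capsules are dispensed.

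*Combined protocol and SAP*

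**What the plan says.** Section 6 (Study Procedures) covers breaking the randomisation code in one paragraph. It gives the circumstances that justify unblinding, then the card, then the route from the on-call team member to the medical supervisor, who decides, with disclosure inside an hour. On the card it says: "A 24/7 emergency mobile contact number will be provided on a wallet-sized card given to participants during their Research Visit".

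Under Subsequent Visits, the same section fixes when that visit happens: "The Research Visit (approximately 2 hours) will take place after day 7 of atorvastatin/placebo administration".

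The capsules leave the site earlier. Section 6 says of randomisation, which falls on the screening day or up to four weeks later: "Randomised participants will be given 7 days of the drug to take home". Section 7a gives one capsule nightly for seven days and adds: "Atorvastatin will be dispensed from the Neurosciences Building, Warneford Hospital by a study medic or nurse". Section 7b says the same for placebo.

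Other text promises contact during the dosing week. Section 8c states: "Participants will have the 24-hour contact phone number of a member of the study team". Section 8d states: "All participants will have 24-hour contact details of a named researcher who they can contact during the study period". Section 6 makes the same promise in the paragraph after the code break, and adds calls on days 2 and 4 and a daily text reminder. None of these places says how or when the number is supplied.

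**The concern.** The card belongs to the code-break procedure, and a code break matters most while the participant is taking blinded capsules. Section 8d confirms that use: when the code is broken, "the participant will be advised to stop taking the medication and withdrawn from the study". That advice has a purpose only if capsules remain to be taken. A card that arrives after the last capsule cannot serve it.

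What a carried card adds to a telephone number is that it can be found by someone else. Section 8c says that participants' "GPs will not be informed about their participation in the study". If a participant is treated outside the study during the week and cannot explain, the treating clinician may have no other sign that a blinded drug is involved. The one-hour disclosure commitment helps only if someone knows to call.

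What is at stake is participant safety, not inference.

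**Working it through.** There is no figure in the plan to reproduce. The check is whether the timing statements fit together, followed by a simple count.

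**Sequence as written**

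| Step | Timing | Source |
|---|---|---|
| Screening Visit | Start | Section 6, Baseline Assessments |
| Randomisation; seven days of capsules taken home | Screening day, or up to 4 weeks later | Section 6, Baseline Assessments |
| Dosing, once nightly | Days 1 to 7 | Sections 7a and 7b |
| Staff telephone calls | Days 2 and 4 | Sections 6 and 8c |
| Research Visit; card handed over | After day 7 | Section 6, code break and Subsequent Visits |

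**Could the Research Visit mean the dispensing contact?** No. It is the named visit under Subsequent Visits at which the behavioural tasks are run. The Sample Handling text in Section 6 also treats the Screening Visit and the Research Visit as two separate occasions for blood sampling.

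**Is an earlier hand-over stated anywhere?** Not in the available text. The card is mentioned once. The 24-hour number is promised in Sections 6, 8c and 8d without a means of supply, so the card is the only means the text describes.

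**What about a participant withdrawn mid-week?** Section 8d withdraws a participant whose code is broken, and Section 6 requires no further procedures after withdrawal. Such a participant need not attend the Research Visit and, on the literal rule, might never receive the card.

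**Count.** Inputs: 50 participants, 25 per arm (Section 9), and 7 dosing days (Section 7).

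- Planned participant-days of dosing: 50 × 7 = 350, or 25 × 7 = 175 per arm.
- Card in hand as written: 50 × 0 = 0 of 350.
- Card in hand if given at dispensing, before the first dose: 50 × 7 = 350 of 350.
- 24-hour number promised: 350 of 350 in both cases.
- Scheduled staff calls: 2 of the 7 days in both cases.

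The count expresses the ordering as participant-days. It does not measure risk.

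**The case against.** The strongest reply is that emergency contact is already covered. Three places promise a 24-hour number for the dosing week or the study period. If the card carries that same number, those promises already imply supply before dosing. If it carries a different one, participants still have a round-the-clock route to the team. Exposure is also modest: seven days of 20 mg of a licensed drug in screened healthy volunteers, with two calls and daily texts. On this view the point is an editorial inconsistency.

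Most of that stands. The protocol as a whole does not plan a week without emergency contact, and the number may be supplied through an appendix or dispensing instructions not seen here. What it does not remove is that the card's one stated hand-over rule puts it after the period it is meant for. Staff work from the written procedure and should not have to guess that something else was intended.

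Two further objections are fair. First, the argument about outside clinicians is partly inference: the text says only that the card carries a number, not that it names the study or drug. Participants are also emailed the information sheet and keep a copy of the consent form (Section 5), and a conscious participant can speak for themselves. The argument therefore bears mainly on someone who is incapacitated. Second, 350 is the planned total. Withdrawn participants are replaced (Section 6), so more than 50 people could take capsules. Neither point changes the order of events.

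**Conclusion.** The concern holds. As written, the emergency card reaches participants after dosing has ended, so it covers none of the seven days for anyone. This conflicts with the code break as Section 8d describes it and sits poorly with the contact promised for the dosing week.

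The conclusion rests on reading the Research Visit as the protocol defines it and on there being no earlier hand-over in text that is not available. It does not rest on any claim that participants would be without a number.

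The wording is most likely a slip, and the other contact provisions limit the consequence. It still should be corrected, because it is a stated safety rule with the wrong timing. Power, type I error and the treatment comparison are untouched.

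**What to change.** In the code-break paragraph of Section 6, replace the reference to the Research Visit as the hand-over point with: *when the study capsules are dispensed, before the first dose*.

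Dispensing is a better point than the Screening Visit, because randomisation can follow screening by up to four weeks. A study medic or nurse already dispenses the capsules in both arms and can hand over the card at the same time.

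The cost is one phrase. No extra visit, material or staff is needed, and blinding and the analysis are unaffected.

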5. PARTICIPANTS

Description of Study Participants
50 healthy volunteers aged 18-50 years
Inclusion Criteria

 • Male or female • Aged 18-50 years • Sufficiently fluent English to understand and complete the tasks • Body Mass Index in the range of 18-30 • Participant is willing and able to give informed consent for participation in the study • Not currently taking any regular medications (except the contraceptive pill)
Exclusion criteria

The participant may not enter the study if any of the following apply:
 
 • Currently any regular medications (except the contraceptive pill) • History or current significant psychiatric illness • Current alcohol or substance misuse disorder • History or current significant hepatic disease • History or current significant neurological condition (e.g. epilepsy) • Known hypersensitivity to the study drug (i.e. atorvastatin) • Pregnant, breast feeding, women of child-bearing potential not using appropriate contraceptive measures • Participation in a study that uses the same or similar computer tasks as those used in the present study • Participation in a study that involves the use of a medication within the last three months
Recruitment

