After a potential volunteer has contacted the research team, they will be sent the Participant Information Sheet via email. We will also send the Participant Information Sheet via email (APPENDIX B: RECONTACT EMAIL TEMPLATE) to participants from previous studies who gave consent to be approached about possible participation in future research studies they may be suitable for. The participant will be given as much time as they need to decide whether they would like to take part and will be invited to ask any questions that they have about the study. If the participant decides that they do not want to take part in the study, they will be thanked for their interest and there will be no further contact from the research team. If the participant decides they would like to take part, they will be invited for a screening visit at the Neurosciences Building, Warneford Hospital. At the beginning of this visit, one of the named researchers will explain the study to the participant and answer any questions that they have. The researcher will then take written consent from the participant. All of the named researchers have been trained in taking informed consent.

Screening and Eligibility Assessment

Informed Consent will be obtained at the start of the screening, prior to the administration of questionnaires or the Structured Clinical Interview for DSM-5 disorders.

A maximum of four weeks will be allowed between screening and randomisation to atorvastatin or placebo. If this duration is exceeded, another screening will need to be performed to ensure eligibility.

At screening, information about demographics, medical history, concomitant medication, and psychiatric history (using Structured Clinical Interview for DSM-5) will be taken (APPENDIX C: SCREENING FORM). Female participants will also have a urine pregnancy test.

Information Provided to Participants and Informed Consent

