6. STUDY PROCEDURES

Baseline Assessments and Procedures

Individuals who are interested in participating in the study will be invited to attend a Screening Visit (maximum 2 hours) at the Neurosciences Building, Warneford Hospital.

Demographic information will be collected:

- Age (years, months), years in full-time education

Participants' eligibility to take part will be checked by recording the following:

- Weight, height, and BMI
- Medical history (including family psychiatric history), details of current and past medication
- Current and prior use of drugs (to exclude for drug use in the three months prior to the study)
- Menstrual cycle (in order to avoid scheduling testing in the premenstrual week)
- SCID-5 interview (Structured Clinical Interview for DSM-5) to probe for current or past psychiatric illness
- Urine pregnancy test (female participants only)

The following baseline assessments will be completed (APPENDIX F: QUESTIONNAIRES):

- Beck Depression Inventory (BDI)
- Eysenck Personality Questionnaire (EPQ)

- Positive and Negative Affect Schedule (PANAS)
- Side-effects questionnaire (to determine baseline of bodily symptoms/'side-effects')
- Snaith-Hamilton Pleasure Scale (SHAPS)
- State and Trait Anxiety Inventory (STAI)
- Visual Analogue Scales (VAS) measuring subjective state

Also, phlebotomy will be undertaken to obtain a sample of:

- high sensitivity-C Reactive Protein

Participants will be asked to wait while their eligibility to take part is assessed by a medical doctor involved in the study (maximum 30 minutes). Any participant for whom additional information is required before an eligibility judgment can be made will be asked to return on a different day once this information has been obtained.

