The behavioural tasks will include the Oxford Emotional Test Battery (ETB), which has previously been found to be sensitive to the effects of antidepressants, and a reward task of Probabilistic Instrumental Learning (PIL). The ETB involves the presentation of emotion-related words and pictures of faces with different expressions. The reward task involves repeatedly choosing between two options and there is the possibility of winning up to £10 depending on the choices made (see 'Expenses and Benefits' below). All stimuli will be presented on a computer screen and participants will be required to respond via button presses on a keyboard.

Participants will be asked to report their adherence to the 7-day administration of atorvastatin/placebo.

At the end of the research visit, a member of the study team will ask participants to try to guess which treatment they received, as a measure of how successful the blinding was.

Sample Handling

Blood samples (4mL = i.e. 1 teaspoon) taken during the Screening Visit and the Research Visit for investigating hs-CRP will be handled at the Neurosciences Building's laboratory. On the same day, they will be rendered acellular by centrifugation on receipt and stored at -30°C until assay. Any excess material remaining at the end of the study will be disposed of by the laboratory within 6 months according to the Human Tissue Authority guidelines. The samples will be stored in a freezer at the Neurosciences Building in an anonymised form. Access to the samples will be by the research team and the samples will be in the custody of [name] who will hold the key code linking the samples to a particular individual. The samples will be analysed for once all participants have completed the study.

Female participants will be required to give a urine sample for a pregnancy test at the Screening Visit. Urine samples will be destroyed immediately after the test result has been obtained.

Discontinuation/Withdrawal of Participants from Study

Each participant has the right to withdraw from the study at any time. In addition, the Investigator may discontinue a participant from the study at any time if the Investigator considers it necessary for any reason including:

- Pregnancy

- Ineligibility (either arising during the study or retrospectively having been overlooked at screening)
- Significant protocol deviation
- Significant non-compliance with treatment regimen or study requirements
- Withdrawal of Informed Consent

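### Women randomised after the screening day can be given capsules on a pregnancy test up to 28 days old; repeating the urine test at dispensing would close this small safety gap.

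*Combined protocol and SAP*

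**What the plan says.** Pregnancy is an exclusion. The criterion in section 5 reads "Pregnant, breast feeding, women of child-bearing potential not using appropriate contraceptive measures". It is checked by a urine test, which is listed in four places: section 5 (Screening and Eligibility Assessment), section 6 (Baseline Assessments and Procedures), section 6 (Sample Handling) and section 8(c). All four tie it to screening; Sample Handling says "Female participants will be required to give a urine sample for a pregnancy test at the Screening Visit". Section 8(c) puts the test among the items recorded to establish that giving the drug is safe.

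The interval between screening and randomisation is set twice, consistently. Section 5 says "A maximum of four weeks will be allowed between screening and randomisation to atorvastatin or placebo", and section 6 says "Randomisation will occur on the day of screening, or up to a maximum of 4 weeks after screening". Section 6 reserves later randomisation for cases where eligibility information is still missing, giving allergy details and previous studies as examples. It adds that "if more than 4 weeks have elapsed, another Screening Visit will be performed to ensure participants are still eligible".

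These participants come back in person: "Any participant for whom additional information is required before an eligibility judgment can be made will be asked to return on a different day". Randomised participants then receive a seven-day supply to take home. On dispensing, section 7 says "Atorvastatin will be dispensed from the Neurosciences Building, Warneford Hospital by a study medic or nurse". The procedures listed for the Research Visit after day 7 repeat the blood sample but include no pregnancy test.

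**The concern.** The 4-week window suits eligibility facts that seldom change within a month, such as allergies or past study participation. Pregnancy status can change within a month. On the deferred route a woman may have a negative test at screening, return up to 4 weeks later, and be handed capsules without a further test, although the plan uses that test to judge whether the drug is safe to give her.

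What is at stake is avoidable exposure of an early pregnancy to up to seven days of atorvastatin 20 mg. The statistical design is not at stake. If a pregnancy came to light after dosing began, section 6 provides only that "the Investigator may discontinue a participant from the study at any time if the Investigator considers it necessary for any reason including" pregnancy. That is discretionary and takes effect after exposure. Her data would be excluded, and she would be replaced, only if she were withdrawn.

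**Working it through.** **Age of the test at dispensing**

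Inputs: test at the Screening Visit only (sections 5, 6 and 8(c)); randomisation from the day of screening to 4 weeks later (sections 5 and 6); re-screening only beyond 4 weeks (section 6); a seven-day supply given to randomised participants (section 6). The documents do not date dispensing separately, so I take it to coincide with randomisation, as section 6 implies.

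- Randomised on the screening day: test age = 0 days.
- Deferred, at the limit: 4 weeks × 7 days = 28 days. This reproduces the plan's own limit. It is a ceiling, not a typical value.
- If the first dose falls on day 28, the seven-day course runs to about 28 + 7 = 35 days after the test.
- With a repeat test on the day of dispensing: test age = 0 days on both routes.

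**How many women, and how many pregnancies**

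The documents give the total (50) and the split (25 per group). They do not give the share deferred, the share of women or the chance of conception. The following are assumptions:

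- share deferred: 10% to 30%;
- share of women: 50%;
- chance of conception over the window, on contraception: 0.1% to 1%.

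| Quantity | Formula | Low | High |
|---|---|---|---|
| Deferred women (test older than the dispensing day) | 50 × 0.5 × share deferred | 50 × 0.5 × 0.10 = 2.5 | 50 × 0.5 × 0.30 = 7.5 |
| Of these, on atorvastatin | × 0.5 (25 of 50) | 1.25 | 3.75 |
| Expected atorvastatin-exposed pregnancies | × chance of conception | 1.25 × 0.001 = 0.00125 | 3.75 × 0.01 = 0.0375 |

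The expected number for the whole study is about 0.001 to 0.04, far below one. It is also an upper bound on what a repeat test could prevent, because a urine test may miss a very recent conception.

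**Do the sections conflict?**

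No. The criterion, the test and the window are consistent with one another. What is absent is a step, on the deferred route only, that renews the pregnancy result before capsules are handed over.

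**The case against.** The best case for leaving the plan alone is that the sponsor chose a 4-week validity window for the whole screening package, pregnancy test included, and requires fresh screening beyond it. Nothing in the documents says that 28 days is too long.

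Other safeguards surround the test. Women of child-bearing potential without appropriate contraception are excluded. The menstrual cycle is recorded at screening. In deferred cases a study doctor's eligibility judgement is itself postponed. Participants are called on days 2 and 4, have a 24-hour contact number and are asked to report changes in health. Pregnancy is a listed ground for discontinuation. Section 8(c) regards the seven-day course as clinically insignificant, and no figure for fetal risk is given. The expected count above is tiny and rests on assumed inputs.

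Much of this stands. The risk is very small, the inputs are assumptions, and the consequence of a seven-day exposure cannot be quantified from the documents. A repeat test would also not detect every early pregnancy, a limit that applies equally to women randomised on the screening day. Because the date of the first dose is not stated, the 0-day figure describes hand-over rather than first exposure.

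These points do not remove the gap. Contraception lowers the chance of pregnancy but does not establish status. The cycle record is made at screening and is there to schedule testing. The later medical judgement is not said to include a new test. The calls come after dosing has begun. None of these re-checks pregnancy status before dispensing. A window set for the package as a whole does not show that a month-old pregnancy result is adequate.

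**Conclusion.** The concern holds as a minor, optional safety improvement. On the deferred route the pregnancy result can be up to 28 days old at dispensing, against 0 days for women randomised on the screening day. The size is small: 2.5 to 7.5 women with an older test and about 0.001 to 0.04 expected exposed pregnancies. Those counts depend wholly on the assumed deferral rate, sex split and conception chance; the 28-day ceiling depends only on the protocol text and on dispensing taking place at randomisation.

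The screening form (Appendix C) is not in the documents, so a dispensing-day check recorded there cannot be ruled out. If one exists, the sponsor need only state it in section 6. Sample size, power and analysis are unaffected.

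**What to change.** Add one sentence to the randomisation paragraph of section 6:

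> Any female participant randomised on a later day than screening will repeat the urine pregnancy test before capsules are dispensed, and a negative result will be recorded at the eligibility sign-off.

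Extend the pregnancy-test sentence under Sample Handling to match, by adding after the reference to the Screening Visit:

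> and again before dispensing if randomised on a later day.

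Same-day randomisation stays as it is.

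The cost is two short text changes and, under the assumptions above, about 3 to 8 extra urine tests (2.5 to 7.5 rounded up). Each takes a few minutes at a return visit the participant already makes, at a site where a medic or nurse already dispenses. No extra visit or staff is needed. The documents do not price the test, so describing the cost as low is a judgement.
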